1.2 Secondary Objectives

1. To describe the 3-year Locoregional Relapse Rate (LRR) in patients treated with organ preservation.
2. To describe the 3-year Distant Relapse Rate (DRR) in patients treated with organ preservation.
3. To describe the 3-year Disease Free Survival (DFS) rate in patients treated with organ preservation.
4. To evaluate the rate of post-operative complications following neoadjuvant FOLFOX/CAPOX and tumour excision/surgery.
5. To evaluate nature, severity and frequency of acute and long term toxicities in all patients.
6. To evaluate Quality of Life (QoL) in all patients.
7. To evaluate the cost-effectiveness of the neo-adjuvant chemotherapy approach vs. the current standard approach.

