3.1.4 Human Toxicology

The most common adverse reactions associated with the combination oxaliplatin/5-FU/LV were peripheral sensory neuropathies, fatigue, myelosuppression, GI toxicity and increased transaminases.

The acute, reversible, primarily peripheral, sensory neuropathy associated with oxaliplatin is of early onset, and can occur within hours or one to two days of dosing. It usually resolves within 14 days, and frequently recurs with further dosing. Symptoms include sensory dysesthesia, paresthesia and hypoesthesia of the limbs, mouth, throat and larynx. Jaw spasm, abnormal tongue sensation, dysarthria, eye pain, and a feeling of chest pressure have also been observed.

Pharyngolaryngeal dysesthesia is common, with severe symptoms in 1-2% of patients shortly after drug infusion. Symptoms usually resolve within hours of onset. The feeling of difficulty in breathing or swallowing may be distressing to the patient. Cold avoidance should be exercised. Treatment is usually not needed, although antihistamines and bronchodilators have been used. To prevent recurrence, infusion time should be extended to 6 hours with subsequent treatments.

The persistent (>14 days), primarily peripheral, sensory neuropathy is usually characterized by paresthesias, dysesthesias, hypoesthesia and altered proprioception. It can interfere with daily activities (e.g. buttoning clothing, holding objects, writing) and occurs in most patients receiving oxaliplatin with 5-FU/LV. Lhermitte's sign and urinary retention are seen rarely. Persistent neuropathy can occur without prior acute neuropathy event. Symptoms may improve in some patients upon discontinuation of oxaliplatin. Calcium gluconate 1 g and magnesium sulphate 1 g infusions pre ± post-oxaliplatin did not appear to be effective neuroprotective agents in a randomized study.

Anaphylaxis has been reported, including severe events in 2-3% of patients, and can occur during any cycle. Patients should not be re-challenged.

Pneumonitis has been reported rarely, and presents with cough, dyspnea, crackles and pulmonary infiltrates; oxaliplatin should be held pending investigation and discontinued if pneumonitis is confirmed.

Incidences of adverse events are generally similar between oxaliplatin used as single agent or with fluorouracil and leucovorin, although severe (grades 3-4) diarrhea, nausea and vomiting, and neurotoxicity are more common with combination therapy.

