LARS and the Fecal Incontinence Quality of Life Instrument		X		X			6, 12, 24 and 36		
Health Economics									
EQ-5D-5L		X	X ¹⁹	X		X	6, 12, 24 and 36		
Phone Contact									
Survival information								X	X
1. Timing for visits after excision are scheduled from last tumour excision date: a. For patients having TME as first protocol excision: from TME date b. For patients having TEMS/TAMIS as first protocol excision: from TEMS/TAMIS date c. For patients having TEMS/TAMIS as first protocol excision and then having a TME: from TME date 2. See protocol section 8 for definitions. 3. Phone contacts or visits after first disease relapse are required every 6 months from date of relapse. 4. Tests may be done on the date of treatment or, if not possible, the previous working day before treatment day. If treatment is to begin on a Monday, may be done on the previous Friday (maximum 72 hours prior to treatment). 5. Please also see protocol Section 12.0 and details for collection, processing, storing, and shipping these samples provided in the CO.28 Correlative Studies Manual. 6. Whole blood (that is not for ctDNA testing) will only be collected prior to enrollment. 7. Not required for patients that had a TME. 8. To be obtained within 28 days as close to the time of relapse as possible. Blood for correlatives done within 28 days PRIOR to date of relapse does not need to be repeated. 9. For CT pelvis and chest, a CT scan with contrast is preferred but not mandated. Patients with contrast allergies may undergo chest X-ray and /or Chest MRI. 10. Contrast is REQUIRED for the CT scan of the abdomen. Patients with contrast allergies may undergo liver ultrasound and /or MRI. 11. Rectal exam and proctoscopy are ideally to be performed by the primary surgeon. Proctoscopy should be performed ≤ 90 days prior to enrollment. Ideally, the surgeon should perform pre and post induction treatment proctoscopies. A gastroenterologist may perform proctoscopy in lieu of the surgeon, but then must also perform the follow-up exam. Proctoscopy may be accomplished using rigid proctoscopy or as part of a flexible sigmoidoscopy or colonoscopy. 12. For patients that had a TME it is only required at month 36. 13. If a rectal tumour tissue biopsy was performed within 90 days prior to enrollment, a repeat biopsy is not necessary. It is recommended that surgeons take a biopsy of the tumour during sigmoidoscopy/colonoscopy to ensure tissue availability and adequate pathology report confirming invasive well-moderately differentiated rectal adenocarcinoma and no evidence of pathologic high risk factors. 14. It is strongly encouraged that suspicious or unequivocal evidence of first local relapse be confirmed definitively by either biopsy (preferred) or by repeat/confirmatory imaging. Where imaging evidence of first local relapse is, in the opinion of the investigator and radiologist, absolutely unequivocal and not requiring subsequent confirmation by either biopsy or follow-up imaging, this must be clearly indicated in supporting documentation. 15. Urine pregnancy test in women of childbearing potential and if a false-positive is suspected this may include an ultrasound to rule-out pregnancy. 16. To be completed daily for patients receiving Capecitabine. 17. Adverse Events to be evaluated using the NCI Common Terminology Criteria for Adverse Events (CTCAE v5.0) (see Appendix III). 18. Only protocol chemotherapy or surgery related adverse events have to be reported after the 30 days post-excision visit. 19. After 3 cycles of FOLFOX or after 2 cycles of CAPOX.									

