7.8.1 Adverse Events

Adverse events (AEs) are recorded in the Adverse Events (AE) sections of CRF Chemotherapy Report, CRF Pre-Excision Report, CRF Surgery Report, CRF Follow Up Report (only AEs thought to be related to protocol treatment), and CRF Short Follow Up Report (ongoing or new grade 3 or higher AEs which are thought to be related to protocol treatment). Severity grade 5 will be combined with grade 4 for the purpose of this report. Adverse events reported during study treatment (in AE sections of CRF Chemotherapy Report, CRF Pre-Excision Report, and CRF Surgery Report) are defined as acute (on treatment) adverse events. Adverse events reported in AE section of CRF Follow Up Report and CRF Short Follow Up Report will be defined as delayed (long term) AEs.

Treatment (capecitabine, oxaliplatin, leucovorin, surgery, and radiotherapy) related adverse events are those events with a relation to protocol therapy of 3=possible,

4=probable or 5=definite.

Severe adverse events are those events reported with a NCI CTCAE Grade of 3 or higher.

The following variables are summarized:

- Acute adverse events: worst CTCAE grade per patient (**Table 32**)
- Severe acute adverse events: worst CTCAE grade per patient (**Table 33**)
- Treatment related acute adverse events: worst CTCAE grade per patient (**Table 34**)
- Delayed severe adverse events: worst CTCAE grade per patient (**Table 35**)

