Dataset: All Accrued Patients		Number of Patients (%) N=**
Patients received neoadjuvant chemotherapy		
No		**(**)
Yes		**(**)
Disease Progression or no response		
Yes		**(**)
Disease Progression		**(**)
No Response based on Pre-excision MRI		**(**)
cT3ab stage		**(**)
node positive disease		** (**)
not clear circumferential radial margin (CRM)		** (**)
No response based on excision specimen		** (**)
node positive disease		**(**)
ypT2		**(**)
ypT1 tumours with:		
- poorly differentiated histology		**(**)
- lymphovascular invasion		**(**)
- positive margin within <1mm		** (**)
Treated with TME		** (**)
No		
Treated with TEMS/TAMIS		** (**)
Ypstage T0/T1 goodN0		
No		** (**)
Subsequent TME		** (**)
Yes		** (**)
Organ Preservation Rate (%) (95% CI)		
Over All Chemotherapy and Excision Treated Patients		** (**-**)
Over All Chemotherapy Treated Patients		** (**-**)

Table 31: Summary of Disease Outcomes

Data set: All Chemotherapy & Excision Treated Patients	Number of Patients (%)
	N=**
Patients who had Disease free survival (DFS) event	** (**)
Locoregional Relapse	**(**)
Site of Disease	
Rectum	**(**)
Pelvis	**(**)
Pelvic Lymph nodes	**(**)
Other	**(**)
Distant Disease	**(**)
Site of Disease	
Lung	**(**)
Liver	**(**)
Brain	**(**)
Distant lymph nodes	**(**)
Skin	**(**)
Ascites	**(**)
Pleural effusion	**(**)
Adrenal glands	**(**)
other	**(**)
Non-protocol therapy without documentation of site of failure	** (**)
Radiotherapy	**(**)
Chemotherapy	**(**)
Biologic therapy	
Death (due to any other reason)	**(**)
Patients who were censored	**(**)
Reason Censored	
Alive at the clinical cut-off	**(**)
Lost to follow-up	**(**)
3 year locoregional relapse rate (%) (95% CI)	**(**-**)
3 year distant relapse rate (%) (95% CI)	**(**-**)
3 year Disease free survival rate (%) (95% CI)	**(**-**)

Figure 2: Kaplan-Meier Curve for Locoregional Relapse Free Survival

Figure 3: Kaplan-Meier Curve for Distant Relapse Free Survival

Figure 4: Kaplan-Meier Curve for Disease Free Survival

Note: Same table and figures will be made for all chemotherapy treated patients.

Table 32: Acute Non-Hematologic Adverse Events

Data set: All Chemotherapy Treated Patients							
	NR	Number of patients (%) N=**					Any grade
		1	2	3	4	5	
Patients with any AE	** (**)	** (**)	** (**)	** (**)	** (**)	** (**)	** (**)
Patients with AE within category							
Category 1 ⁽¹⁾	**(**)	**(**)	**(**)	**(**)	**(**)	**(**)	**(**)
Event 1	**(**)	**(**)	**(**)	**(**)	**(**)	**(**)	**(**)

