Event 2	**(**)	**(**)	**(**)	**(**)	**(**)	**(**)	**(**)
Event 3	**(**)	**(**)	**(**)	**(**)	**(**)	**(**)	**(**)
...							
Category 2 ⁽¹⁾	**(**)	**(**)	**(**)	**(**)	**(**)	**(**)	**(**)
Event 1	**(**)	**(**)	**(**)	**(**)	**(**)	**(**)	**(**)
...							

(1) Patients may have more than one event within a category.

Table 33: Severe Acute Non-Hematologic Adverse Events

Data set: All Chemotherapy Treated Patients					Any grade 3 or higher AE	
		Number of patients (%) N=**				
		3	4	5		
Patients with any AE		** (**)	** (**)	** (**)	** (**)	
Patients with AE within category						
Category 1 ⁽¹⁾		**(**)	**(**)	**(**)	**(**)	
Event 1		**(**)	**(**)	**(**)	**(**)	
Event 2		**(**)	**(**)	**(**)	**(**)	
Event 3		**(**)	**(**)	**(**)	**(**)	
...						
Category 2 ⁽¹⁾		**(**)	**(**)	**(**)	**(**)	
Event 1		**(**)	**(**)	**(**)	**(**)	
...						

(1) Patients may have more than one event within a category.

Table 34: Acute (On-treatment) Adverse Events Related to Oxaliplatin for Patients on FOLFOX

Data set: All Chemotherapy Treated Patients							
		Number of patients (%) N=**					
		Worst grade					Any grade
		NR	1	2	3	4	5
Patients with any drug related AE	** (**)	** (**)	** (**)	** (**)	** (**)	** (**)	** (**)
Patients with AE within category							
Category 1 ⁽¹⁾	**(**)	**(**)	**(**)	**(**)	**(**)	**(**)	**(**)
Event 1	**(**)	**(**)	**(**)	**(**)	**(**)	**(**)	**(**)
Event 2	**(**)	**(**)	**(**)	**(**)	**(**)	**(**)	**(**)
Event 3	**(**)	**(**)	**(**)	**(**)	**(**)	**(**)	**(**)
...							
Category 2 ⁽¹⁾	**(**)	**(**)	**(**)	**(**)	**(**)	**(**)	**(**)
Event 1	**(**)	**(**)	**(**)	**(**)	**(**)	**(**)	**(**)
...							

(1) Patients may have more than one event within a category.

NOTE: Same type of table to be made on adverse events related to leucovorin and 5FU for patients on FOLFOX, to oxaliplatin and capecitabine for patients on CAPOX, to surgery for patients who received surgery, and to radiotherapy for patients who received radiotherapy.

Table 35: Severe Delayed Non-Hematologic Adverse Events

Data set: All Chemotherapy Treated Patients							
		Number of patients (%) N=**					
		Worst grade			Any grade 3 or higher AE		
		3	4	5			
Patients with any AE		** (**)	** (**)	** (**)	** (**)		
Patients with AE within category							
Category 1 ⁽¹⁾		**(**)	**(**)	**(**)	**(**)		
Event 1		**(**)	**(**)	**(**)	**(**)		
Event 2		**(**)	**(**)	**(**)	**(**)		
Event 3		**(**)	**(**)	**(**)	**(**)		
...							
Category 2 ⁽¹⁾		**(**)	**(**)	**(**)	**(**)		

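### Late adverse events are tabulated only at grade 3 or higher, so grade 1-2 toxicity recorded in follow-up appears in no adverse-event table and the long-term toxicity objective is met only for severe events

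*SAP*

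**What the plan says.** Protocol 1.2, objective 5, repeated in SAP 3.2, is "To evaluate nature, severity and frequency of acute and long term toxicities in all patients". It sets no grade limit. SAP 4.3 counts non-serious as well as serious adverse events among the safety endpoints.

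On collection, the Protocol 5.0 flowsheet schedules adverse-event assessment at months 6, 12, 18, 24, 30 and 36 after excision. Its note 18 reads "Only protocol chemotherapy or surgery related adverse events have to be reported after the 30 days post-excision visit". That limits by relatedness, not by grade. SAP 7.8.1 describes the source form in the same way: "CRF Follow Up Report (only AEs thought to be related to protocol treatment". Only the Short Follow Up Report is restricted to grade 3 or higher. SAP 7.8.1 classes everything on these two forms as delayed, and everything on the Chemotherapy, Pre-Excision and Surgery Reports as acute.

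On reporting, the one delayed summary is "Delayed severe adverse events: worst CTCAE grade per patient", and its shell is "Table 35: Severe Delayed Non-Hematologic Adverse Events". The all-grade shells are "Table 32: Acute Non-Hematologic Adverse Events" and Table 34 with its companions by drug and modality. All of these are for acute events.

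On expected toxicity, Protocol 3.1.4 describes "The persistent (>14 days), primarily peripheral, sensory neuropathy" and says that it "occurs in most patients receiving oxaliplatin with 5-FU/LV". It gives no grade.

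**The concern.** An objective that asks how severe and how frequent late toxicity is cannot be fully answered from a table that starts at grade 3. Oxaliplatin neuropathy is the clearest example. Protocol 3.1.4 separates an acute form, which usually resolves within 14 days and returns with further doses, from a persistent form that can interfere with everyday tasks. Late grade 1-2 neuropathy is the kind of event this objective should describe, and it has no place in the tables.

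The gap bears on interpretation. Protocol 2.0 favours the chemotherapy strategy partly because the chemoradiation alternative carries more long-term toxicity, and its Table 1 gives TME alone as standard treatment for cT1N0 and cT2N0. A late-toxicity display limited to grade 3 or higher could make the strategy look cleaner than the collected data would.

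**Working it through.** No figure in the plan needs reproducing here. The check traces each source form to the table shells.

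| Source form (SAP 7.8.1) | Class | Grades collected | Grade 1-2 shown | Grade 3+ shown |
|---|---|---|---|---|
| Chemotherapy, Pre-Excision and Surgery Reports | Acute | All | Tables 32, 34 and companions | Tables 32, 33, 34 and companions |
| Follow Up Report | Delayed | Related events, no stated floor | None | Table 35 |
| Short Follow Up Report | Delayed | Related events, grade 3+ only | Not collected | Table 35 |

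The second row is the gap: grade 1-2 delayed events are collected and appear in none of the adverse-event tables.

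**How much neuropathy the acute tables cover.** FOLFOX is 6 cycles of 14 days, so the last cycle starts at 5 × 2 = 10 weeks. CAPOX is 4 cycles of 21 days, so the last cycle starts at 3 × 3 = 9 weeks. Protocol 7.3 places excision up to 5 weeks (FOLFOX) or 6 weeks (CAPOX) after the first dose of the last cycle. The acute window therefore runs to about 10 + 5 = 15 or 9 + 6 = 15 weeks from the first dose. Persistent in Protocol 3.1.4 means only more than 14 days, so much persistent neuropathy would arise inside that window and be shown at all grades.

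**What the acute tables cannot show.** Worst grade per patient over that window does not separate neuropathy that resolved between cycles from neuropathy that lasted. It says nothing about continuation or onset during follow-up.

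**The 30-day visit.** SAP 7.9 takes medication data from 30 days after excision from the Follow Up Report. If adverse events at that visit are recorded on the same form, grade 1-2 events there are also classed as delayed and left out. This is an inference, because the forms are not in the documents.

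**Other instruments.** QLQ-C30, CR29, LARS, FIQL and EQ-5D-5L contain no item on numbness or tingling. QLQ-C30 question 6 and the EQ-5D usual-activities item could register interference with daily life, but without attributing it to neuropathy.

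**Hematologic wording.** SAP 7.8.1 lists the summaries for Tables 32, 33 and 35 without a hematologic exclusion, while all three titles carry one. Protocol 7.1.3.1 places febrile neutropenia under blood and lymphatic disorders, and Table 36 grades laboratory counts only. Read literally, the titles of Tables 32 and 33 would omit febrile neutropenia.

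**The case against.** The best defence of the grade 3 cut is consistency. Delayed events pool two forms, and the Short Follow Up Report, used after relapse or failure and for patients with no protocol excision, takes only grade 3 or higher. Grade 3 is thus the one threshold ascertained in every patient throughout follow-up. That is a good reason to keep Table 35 and to footnote any all-grade table. It is not a reason to leave the grade 1-2 events on the Follow Up Report untabulated.

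A reader might go further and infer that low-grade neuropathy is never reported, that the objective is unanswered, or that most of the 58 accrued patients would have late neuropathy missing from the tables while Table 35 sat near zero. The documents support none of these:

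- Neuropathy up to surgery is shown at all grades, and severe late events are shown.
- The statement about most patients in Protocol 3.1.4 concerns oxaliplatin with 5-FU/LV. It gives no grade and no duration beyond 14 days.
- Protocol 2.0 expects the shortened course to reduce toxicity.
- The safety population is the chemotherapy-treated patients, whose number is not given.

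The hematologic point is also limited. No blood counts are scheduled after the pre-excision visit, so little routine late hematology is lost. Febrile neutropenia can still appear in Table 34 and its companions, and in Table 42 if it ended chemotherapy. The SAP does not define non-hematologic, so the titles may be meant only to set laboratory counts apart. What stands is that text and titles disagree.

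**Conclusion.** The point holds as a reporting gap. Followed as written, the SAP leaves grade 1-2 toxicity collected on the Follow Up Report out of every adverse-event table, and objective 5 is met for acute toxicity at all grades but for late toxicity only at grade 3 or higher. The number of patients affected cannot be derived from the documents; any count would need an assumed rate of late grade 1-2 events. The conclusion rests on taking the SAP's description of the forms at face value. It does not touch the primary endpoint, the two-stage rule or any efficacy estimate. The change is worth making because late toxicity is a stated objective and matters to how the strategy is judged. The mismatch between SAP text and table titles is secondary.

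**What to change.** - Add an all-grade table of delayed treatment-related adverse events from the Follow Up Report, worst grade per patient, in the chemotherapy-treated population.
- Where the form records it, add sensory neuropathy grade at each scheduled follow-up visit (months 6, 12, 18, 24, 30 and 36), with the number of patients assessed at each.
- Footnote that Short Follow Up Report data, after relapse or with no protocol excision, are grade 3 or higher only, so grade 1-2 ascertainment is incomplete for those patients.
- Keep Table 35.
- Reconcile SAP 7.8.1 with the titles of Tables 32, 33 and 35 by stating that clinically reported events such as febrile neutropenia are kept there and that only laboratory-graded counts are shown separately.

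The cost is one extra table, a footnote and a clarifying sentence. The all-grade table uses data the SAP says are already collected. Whether neuropathy grade is available by visit must be checked against the form.

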7.8.2 Laboratory Evaluations

Laboratory evaluations, except coagulation and CEA, reported on CRF Chemotherapy Report and CRF Pre-Excision Report will be included in the calculation laboratory adverse events. Coagulation is only reported on CRF Pre-Excision Report and CEA on CRF Pre-Excision Report and of CRF Follow Up Report, which will be summarized individually. Laboratory results will be classified according to the NCI CTCAE when available.

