7.1.3 Dose Adjustments

Doses will be reduced for hematologic and other adverse events. Dose adjustments are to be made according to the system showing the greatest degree of toxicity. Adverse events will be graded using the NCI Common Terminology Criteria for Adverse Events (CTCAE) (see Appendix III).

The major toxic effects which limit dose are hematologic. The guidelines which follow outline dose adjustments for several of these toxic effects. If a patient experiences several adverse events and there are conflicting recommendations, please use the recommended dose adjustment that reduces the dose to the lowest level.

7.1.3.1 *FOLFOX*

The precise dose modification schema used and the symmetry of dose modification (e.g., reduce both 5FU and oxaliplatin symmetrically, or one preferentially) may be left to the discretion of the treating oncologist. **The modification schema in Table Dose levels of FOLFOX is a guideline.** Leucovorin dose may be decreased in concert with bolus 5-FU dose. If 5-FU is not administered, leucovorin should not be administered.

1. **Dose reduction:** If a patient requires a dose reduction below level -2 during cycles 1-5 preoperative therapy, consider discontinuing FOLFOX and referring the patient for TME. This does not apply for cycle 6.
2. **Dose delay:** If FOLFOX is held due to toxicity for more than 30 days from planned next cycle date consider discontinuing FOLFOX and referring the patient for TME. This does not apply for cycle 6.

Dose levels of FOLFOX

Dose Level*	5-FU infusion	5-FU bolus	Oxaliplatin
0	1200 mg/m ² /day x 2 days (2400 mg/m ² over 46-48 hours)	400 mg/m ²	85 mg/m ²
-1	960 mg/m ² /day x 2 days (1920 mg/m ² over 46-48 hours)	320 mg/m ²	65 mg/m ²
-2	800 mg/m ² /day x 2 days (1600 mg/m ² over 46-48 hours)	270 mg/m ²	50 mg/m ²
-3**	680 mg/m ² /day x 2 days (1360 mg/m ² over 46-48 hours)	230 mg/m ²	40 mg/m ²

* Dose level 0 refers to the starting dose.
 ** If dose reduction below level -2 is required during cycles 1-5 of neoadjuvant therapy for a Group 1 patient, FOLFOX should be discontinued and the patient referred for standard surgical therapy. Dose reduction to level -3 is only permitted during cycle 6.

Suggested FOLFOX Dose Modifications Based on Interval Adverse Events

The following describe actions in the Dosage Change column:

- Omit = Treatment is not given for this cycle
- Hold = Treatment can be made up as part of this cycle
- Discontinue = Treatment is totally stopped

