7.8.2.1 Hematology

- Hemoglobin, WBC, absolute neutrophil count (ANC), neutrophils, platelets, lymphocytes, basophils, monocytes, eosinophils: worst CTCAE grade per patient (**Table 36**)

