Grade 1	** (**)
Grade 2	** (**)
Grade 3	** (**)
Grade 4	** (**)
Not reported ⁽¹⁾	** (**)
Creatinine Clearance	
Grade 0	** (**)
Grade 1	** (**)
Grade 2	** (**)
Grade 3	** (**)
Grade 4	** (**)
Not reported ⁽¹⁾	** (**)

⁽¹⁾ Not done or outside the 30-day window prior to enrollment

Table 10: Baseline Coagulation

Data set: All Accrued Patients	
	Number of Patients (%)
	Total N=**
PT	
Grade 0	** (**)
Grade 1	** (**)
Grade 2	** (**)
Grade 3	** (**)
Grade 4	** (**)
Not reported ⁽¹⁾	** (**)
INR	
Grade 0	** (**)
Grade 1	** (**)
Grade 2	** (**)
Grade 3	** (**)
Grade 4	** (**)
Not reported ⁽¹⁾	** (**)
PTT	
Grade 0	** (**)
Grade 1	** (**)
Grade 2	** (**)
Grade 3	** (**)
Grade 4	** (**)
Not reported ⁽¹⁾	** (**)

⁽¹⁾ Not done or outside the 30-day window prior to enrollment

Table 11: Baseline Symptoms Status

Data set: All Accrued Patients						
	Number of patients (%) N=**					
	Worst grade	Any grade				
Patients with any symptom/finding at baseline	NR ** (**)	1 ** (**)	2 ** (**)	3 ** (**)	4 ** (**)	** (**)
Patients with particular symptom/finding, within body system:						
Body System 1 ⁽¹⁾	**(**)	**(**)	**(**)	**(**)	**(**)	**(**)
Event 1	**(**)	**(**)	**(**)	**(**)	**(**)	**(**)
Event 2	**(**)	**(**)	**(**)	**(**)	**(**)	**(**)
Event 3	**(**)	**(**)	**(**)	**(**)	**(**)	**(**)
...	**(**)	**(**)	**(**)	**(**)	**(**)	**(**)
Body System 2 ⁽¹⁾						
Event 1	**(**)	**(**)	**(**)	**(**)	**(**)	**(**)
...	**(**)	**(**)	**(**)	**(**)	**(**)	**(**)
()	**(**)	**(**)	**(**)	**(**)	**(**)	**(**)

⁽¹⁾ Patients may have more than one event within a body system

Table 12: Prior Concomitant Medications (Baseline)

Data set: All Accrued Patients	
	Number of patients (%)
	N=**
Any prior concomitant medication ⁽¹⁾	
No	** (**)
Yes	** (**)
Drug Name 1	** (**)
Drug Name 2	** (**)
....	

Table 13: Past or Current Major Medical Problems

Data set: All Accrued Patients	
	Number of patients (%)
	N=**
Patients Reporting at least one past or current major medical problem at baseline	
Medical Problem ⁽¹⁾	** (**)
...	** (**)

(1) patients may report more than one medical problem reported

Table 14: Tobacco Smoking History at Baseline

Data set: All Accrued Patients		Number of patients (%) N=**
Ever smoked any tobacco product		
Yes		** (**)
No		** (**)
Unknown		** (**)
Currently smoking		
Yes		** (**)
No		** (**)
Current Average number of cigarettes per day		
N		**
Median		**
Min - Max		** - **
Years from quitting smoking to enrollment		
N		**
Median		**
Min - Max		** - **

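### Laboratory toxicity is tabulated without the baseline grades the trial collects, and no all-cause row counts patients with any grade 3 or higher event

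*SAP*

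**What the plan says.** **Laboratory values.** Under SAP 7.8.2, results other than coagulation and CEA that are reported on the chemotherapy and pre-excision forms "will be included in the calculation laboratory adverse events". SAP 7.8.2.1 (hematology) and 7.8.2.2 (biochemistry) give the metric as "worst CTCAE grade per patient". The shells of Tables 36 and 37 have one block per parameter, with no baseline column and no row that combines parameters. Baseline grades are planned elsewhere: Table 8 for hematology, Table 9 for biochemistry and, for clinical findings, "Table 11: Baseline Symptoms Status". Among the safety laboratory measures, only CEA is analysed as change from baseline (SAP 7.8.2.3).

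**Clinical events.** Under SAP 7.8.1, events reported during study treatment "are defined as acute (on treatment) adverse events", with no condition that they be new or worse than at baseline. The list of summaries there opens with "Acute adverse events: worst CTCAE grade per patient" for Table 32. It goes on to severe acute events (Table 33), treatment-related acute events (Table 34) and delayed severe events (Table 35), and excludes no body system. The first shell, however, is headed "Table 32: Acute Non-Hematologic Adverse Events". Tables 33 and 35 carry the same restriction in their titles. All three shells have a row for patients with any AE.

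**Protocol.** Section 7.1.3 states: "The major toxic effects which limit dose are hematologic". The FOLFOX modification table in 7.1.3.1 places febrile neutropenia under blood and lymphatic disorders, apart from its rows for other non-hematologic events.

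**The concern.** The fifth secondary objective is the nature, severity and frequency of toxicity in all patients. In a single-arm trial these tables are the whole answer, because no comparator carries the same background of disease.

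Two things then go wrong. A laboratory abnormality that the patient brought into the trial is reported as a laboratory adverse event of the trial. And a reader who wants the share of patients with severe toxicity will go to the any-AE row of Table 33. By its title, that row leaves out the class of toxicity that the protocol describes as dose-limiting, and no other all-cause row supplies the full count.

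**Working it through.** The plan states no toxicity rate, so there is no figure to reproduce. The check compares text with shells, then uses assumed rates to show the possible size.

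**1. Can baseline anaemia enter Table 36?** Protocol 4.1.9 limits ANC, platelets, bilirubin and creatinine clearance at entry. It sets no hemoglobin limit. Table 36 takes the worst on-treatment grade. A patient with grade 1 hemoglobin at entry and throughout treatment is therefore counted as grade 1 in Table 36.

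**2. Size for the any-grade hemoglobin row (assumed rates).** Let b be the share of patients with grade 1 or higher at baseline. Let w be the chance of onset or worsening on treatment, taken as equal whether or not the patient was anaemic at entry. Assume also that no patient anaemic at entry improves to grade 0 for the whole of treatment.

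- Table 36 shows b + (1 − b)w.
- A count of patients worse than baseline shows w.
- The excess is b + (1 − b)w − w = b(1 − w).

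Excess in percentage points:

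| b | w = 20% | w = 40% | w = 60% |
|---|---|---|---|
| 10% | 8 | 6 | 4 |
| 20% | 16 | 12 | 8 |
| 40% | 32 | 24 | 16 |

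With 58 patients, the accrual in SAP 2.2, the extremes are 58 × 0.04 = 2.3 and 58 × 0.32 = 18.6 patients. At b = 20% and w = 40%, Table 36 shows 0.20 + 0.80 × 0.40 = 52% against 40% worse than baseline. The difference is 58 × 0.12 = 7 patients.

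**3. Can a reader correct this by setting Table 8 beside Table 36?** No. In the last example, subtracting the two margins gives 52 − 20 = 32%, not 40%, because some patients anaemic at entry also worsen. The margins do not show who changed. The data sets differ too: Table 8 uses all accrued patients and Table 36 uses chemotherapy patients.

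**4. Is there an all-cause count of patients with any grade 3 or higher event?**

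- Table 33: severe acute events, titled non-hematologic.
- Table 35: severe delayed events, titled non-hematologic. SAP 7.8.1 limits follow-up reporting to events thought related to treatment, so this table is not all-cause in any case.
- Table 36: each parameter separately.
- Table 34 and its companions: no hematologic restriction, but attributed events only.

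The overlap between Table 33 and the blocks of Table 36 cannot be recovered from the printed tables, so the combined number cannot be derived from them.

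**5. Size for the severe row (assumed rates).** Let a be the share with a severe non-hematologic event and h the share of the remainder with only a severe hematologic one. The number outside the Table 33 row is 58 × (1 − a) × h. For a = 20-40% and h = 5-20%, this runs from 58 × 0.60 × 0.05 = 1.7 to 58 × 0.80 × 0.20 = 9.3 patients, or about 2 to 9. Each patient is 1/58 = 1.7 percentage points.

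**6. Where can febrile neutropenia appear?** The protocol defines it by a neutrophil count together with a temperature, so it is not a laboratory grade, and Table 36 has no row for it. It fits the Table 34 series if attributed to treatment, and Table 42 if it leads to stopping chemotherapy. Its place in Tables 32 and 33 is unclear.

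**The case against.** Worst-grade tables are routine. Baseline grades are not hidden, since Tables 8, 9 and 11 stand in the same report. Entry limits on ANC, platelets, bilirubin and creatinine clearance confine the baseline problem mainly to low-grade hemoglobin. Hematologic toxicity is reported, in Table 36, and the any-AE rows sit under titles that state their restriction. The tables are descriptive and no decision rule uses them. All of that is fair. It limits the consequences, but it supplies neither a within-patient comparison with baseline nor a combined severe count.

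The objection also blocks some stronger readings that a reader might infer:

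- **That febrile neutropenia is definitely excluded from Tables 32 and 33, or is visible only when attributed to treatment.** The SAP does not define non-hematologic. The titles may be meant only to separate reported events from laboratory-derived ones, and the protocol's dose table is not the SAP's coding scheme. Table 42 is a further route that does not depend on attribution. What the documents establish is a conflict between text and titles.
- **That tumour symptoms present at entry are counted as toxicity.** This happens in Tables 32 and 33 only if sites re-enter unchanged baseline symptoms as on-treatment events. The form instructions are not in the documents.
- **That any event not above its baseline grade should be dropped.** That would remove events that resolve and recur at the same grade. In Tables 34 and 35 it would remove events attributed to treatment.

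**Conclusion.** The point holds in two parts, and both should be settled before the database lock that SAP 2.2 describes as still to come.

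First, Tables 36 and 37 present worst grades as laboratory adverse events without reference to baseline. The effect is clearest for hemoglobin. Its size is unknown: 4 to 32 percentage points on the any-grade row rests wholly on the assumed 10-40% baseline anaemia and 20-60% onset or worsening, and on no complete improvement during treatment.

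Second, the SAP 7.8.1 text and the titles of Tables 32, 33 and 35 disagree on scope, and no all-cause row counts patients with any grade 3 or higher toxicity. The figure of about 2 to 9 patients is likewise an illustration. It uses the accrual of 58, while the tables use chemotherapy-treated patients, whose number is not given.

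The effect is on a secondary, descriptive objective. The organ preservation analysis and its decision rule are untouched.

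**What to change.** - **Laboratory values.** Keep Tables 36 and 37. Beside them, add baseline grade by worst on-treatment grade for each parameter, and report the number of patients whose grade became worse than baseline.
- **Clinical events.** Make Tables 32, 33 and 35 cover all reported clinical adverse events, febrile neutropenia included, so that titles and the SAP 7.8.1 text agree.
- **Overall severity.** Add one row: patients with any grade 3 or higher event, whether clinical or a laboratory grade worsened from baseline.
- **Baseline symptoms.** In Tables 32 and 33, flag clinical events that were present at baseline at the same or a higher grade, and do not remove them. Leave the treatment-related tables (the Table 34 series and Table 35) unfiltered.

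The cost is modest programming and slightly longer tables. All the data are already collected.
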